2.5 Statistical Interim Analyses and Stopping Guidance

There will be no interim analyses in this trial.

2.6 Timing of Final Analysis

The main analysis is planned when all patients are finished with the data collection, all data have been entered, verified and validated and the primary database has been locked.

2.7 Timing of Outcome Assessments

Outcomes are assessed at baseline, 3 and 6 months. In addition, the intervention group will answer questionnaires as part of the Happy Hands app at a monthly basis and after each exercise session.

Visit Label	Target Day	Definition (Day window)
T0. Consent	The day they consult a healthcare provider at one of the recruitment sites	Day 0
T0. Randomization	After receiving information about the study, the participants are asked to sign a digital consent, thereafter the participants are randomly allocated to two groups based	Day 0

Statistical Analysis Plan Happy Hands Diakonhjemmet Hospital

Page 12 of 27

	on baseline questionnaire (see section 2.2.)	
TO. Baseline	Day 0 Baseline assessment	Day 0
T3. 3-months follow-up	Day 90 Follow-up (digital/face- to-face)	Day 90 +/- 45
T6. 6-months follow-up	Day 180 Follow-up (digital)	Day 180 +/- 45

3. Statistical Principles

3.1 Adherence and Protocol Deviations

3.1.1 Adherence to Allocated Treatment e-self-management intervention:

Adherence will be evaluated by tracking the number of exercise and informational videos viewed, as well as the number of quizzes completed each week. Each time a participant watches a video or submits quiz answers; this activity will be recorded in Nettskjema. Participants will also document each instance of exercise completion in the app. Recognizing that not all participants will view the same exercise videos multiple times, adherence to the exercise regimen will be based on self-reported exercise completion. As there is no consensus regarding what constitute adequate adherence to hand exercises, the American College of Sports Medicine guidelines will be used [17]. Adherence to the exercise program will be considered adequate if participants compete ≥2 exercise sessions per week for a duration of least 8 weeks (67%)[18]. Adherence to information videos and quizzes will be deemed adequate if participants have watched 19 of 26 videos and completed 9 of 12 quizzes, corresponding to approximately 75% utilization.

Usual care:

Usual care will vary between the different recruitment sites, from nothing to a single consultation, information courses or adaptation of orthosis. Thus, all participants are considered to have received usual care.

3.1.2 Protocol Deviations

Not all recruitment sites have the possibility to summon the participants for a face-to-face follow-up consultation. Thus, there will be a deviation from the protocol regarding the assessment of follow-up grip strength.

Statistical Analysis Plan Happy Hands Diakonhjemmet Hospital

Page 13 of 27

3.2 Analysis Populations

The Enrolled set will include all patients who have provided informed consent, have been included into the study data base, randomly assigned to one of the two groups and completed the baseline questionnaire.

The Full Analysis Set will be the same as the Enrolled set as the different questionnaires are linked together at baseline, thus, the patients will answer both consent, baseline questionnaire and be randomly allocated in one action.

The Per protocol set will include those who are deemed adherent based on the number of exercise session they have conducted and the number of informational videos they have seen.

4. Trial Population

4.1 Screening Data, Eligibility and Recruitment

The total number of screened patients and reasons for not entering the trial will be summarised and tabulated.

A CONSORT flow diagram (Figure 3) will be used to summarise the number of patients who were:

- assessed for eligibility at screening
- eligible at screening
- ineligible at screening
- eligible and randomised
- eligible but not randomised
- received the randomised allocation
- lost to follow-up 3 months
- lost to follow-up 6 months

Reasons will be provided where possible.

Statistical Analysis Plan Happy Hands Diakonhjemmet Hospital

4.2 Withdrawal/Follow-up

The status of eligible and randomised patients at trial end will be tabulated by group according to

- withdrawn consent
- lost to follow-up

This will be presented in the CONSORT diagram.

4.3 Baseline Patient Characteristics

The patient demographics and baseline characteristics to be summarised include age, gender, living arrangement, education, occupational status, smoking, height and weight (calculated to BMI), most painful hand, other painful joints, previous treatment including surgery, medication, comorbidities, (e)Health literacy, joint mobility, pain at rest and in activity, disease activity, hand function, quality of care, health-related quality of life, motivation for exercising, grip strength.

Patient demographics and baseline characteristics will be summarised by randomised treatment arm and overall using descriptive statistics (mean, standard deviation, median, 25/75 percentiles) for continuous variables, and number and percentages for categorical variables. Any clinically important imbalance between the treatment groups will be noted.

5. Analysis

5.1 Outcome Definitions

5.1.1 General Definitions and Derived Variables

5.1.1.1 Age Reported as age in years

5.1.1.2 Gender Reported as male/ female/ other.

5.1.1.3 Living arrangements

Reported as living alone / living together with someone.

5.1.1.4 Education

Reported as elementary school / high school / college, university less than 4 years / college, university 4 years or more. Will be dichotomized into less than (elementary school/ high school) or more than (college, university) 12 years.

Statistical Analysis Plan Happy Hands Diakonhjemmet Hospital

Page 16 of 27

5.1.1.5 Occupation status

Reported as working fulltime / working parttime / fulltime sick leave / parttime sick leave / retired / disability benefit / work assessment allowance / seeking work / unpaid, staying at home /student. Will be dichotomized to working/ not working.

5.1.1.6 Smoking

Reported as smoking/ smoking previously/ not smoking.

5.1.1.7 Height and weight (Body mass index, BMI)

Reported as body height (cm) and body weight (kg). Calculated as BMI = Body weight in kilograms divided by the square of the height in meters.

5.1.1.8 Most troublesome joint

Reported as left hand/ right hand/ both hands/ none of the hands.

5.1.1.9 Other troublesome joints

Reported as right hip/ left hip/ right knee/ left knee/ right ankle or foot/ left ankle or foot. Will be summarized into number of other troublesome joints (0-6)

5.1.1.10 Previous treatment

Reported as having received previous treatment (yes/no) and a description of the treatment if reporting yes. Additionally, reported as previously having hand surgery (yes/no), and if yes, with hand (right/ left / both).

5.1.1.11 Medication

Reported as using medication due to hand OA (yes/no), with description of type and dose if answering yes.

5.1.1.12 Comorbidities

Reported as any problems affecting health (yes/no) for the following reasons: high blood pressure/ angina, infarction, other heart disease/ asthma, bronchitis, other lung disease/ allergy, eczema/ sciatic pain/ stroke, cerebral haemorrhage/ cancer/ neurological disease/ diabetes/ metabolic disease/ mental disease/ kidney disease/ liver disease/ ulcer, other stomach disease/ anaemia. Summarized as having comorbidity (yes/no), and number of comorbidities (0-15).

5.1.1.13 (e)Health literacy

Measured by eHEALS [19,20], consisting of eight statements answered on 5-point scale (from "totally agree" to "totally disagree") with a total score ranging from 8 to 40 (higher score representing higher health literacy). Additionally, the participants are asked about their knowledge/experience with using technology and digital services like smartphone, tablets, apps, video consultation, and digital services (Helsenorge.no). The knowledge/experience with using measured on a 5-point scale (very poorly to very good) with an additional alternative of 'never tried'

5.1.1.14 Joint mobility

Measured using a numeric rating scale (NRS) from 0 to 10 with 0 being very good joint mobility. Reported separately for left and right hand. In baseline, 3- and 6-month questionnaires, the

Statistical Analysis Plan Happy Hands Diakonhjemmet Hospital

Page 17 of 27

participants are asked to rate their pain the last week. In the Happy Hands app, the participants are asked to rate their pain after exercising.

5.1.1.15 Pain

Measured using an NRS from 0 to 10 with 0 being no pain. Reported separately for right and left hand at rest and in activity. In baseline, 3- and 6-month questionnaires, the participants are asked to rate their pain the last week. In the Happy Hands app, the participants are asked to rate their pain after exercising.

5.1.1.16 Disease activity

Measured using an NRS from 0 to 10 with 0 being no disease activity.

5.1.1.17 Hand function

Measured by the Measure of Activity of the Hand (MAP-Hand) questionnaire, containing 18 questions about problems with different activities (no problems/ some problems/ large problems /cannot perform). A mean score (from 1 to 4 with 1 being no problems) is calculated from the answers, with at least 15 of 18 items having to be answered for a valid score [21].

5.1.1.18 Quality of care

Measured by a modified version of the OsteoArthritis Quality Indicator questionnaire v2 [22], modified to hand OA. Containing 20 items related to treatment recommendations for hand OA, answered with yes/no/not relevant, do not have pain, do not remember. Scored as a pass rate (0-100%, with 100% being best quality of care), calculated as the number of yes-answers, divided by the total number of yes- and no-answers.

5.1.1.19 Health-related quality of life

Measured by EuroQol EQ-5D-5L [23], five items (mobility, self-care, usual activities, pain/discomfort, anxiety/depression) scored at a 5-level scale ("no problems" to "unable to do"), calculated as a utility index 0-1, 1= best health-related quality of life. Visual analogue scale (EQ VAS), 0-100, 100= perfect health.

5.1.1.20 Grip strength

Maximum grip strength measured as the mean of two measures for left and right hand separately, using the JAMAR dynamometer. Grip strength is given in kg.

5.1.1.21 Motivation for exercising

Reported on an NRS from 0 to 10 with 0 being no motivation.

5.1.1.22 Costs

Costs connected to patient care pathways will be self-reported by the patient using open-ended questions.

5.1.2 Primary Outcome Definitions

The primary outcome will be defined as OMERACT/OARSI responder [24], which is a composite index reported as a single variable (yes/no) based on one of the two following criteria:

Statistical Analysis Plan Happy Hands Diakonhjemmet Hospital

Page 18 of 27

- High improvement on pain or function
 - \circ ≥50% improvement + absolute change of ≥2 points in pain (NRS 0-10, 0=no pain), OR
 - ≥50% improvement + absolute change of ≥0.6 point in hand function (MAP-Hand 1-4, 1=no disability)
- Improvement in at least two of the three following
 - ≥20% improvement + absolute change of ≥1 points in pain (NRS 0-10, 0=no pain)
 - ≥20% improvement + absolute change of ≥0.3 point in hand function (MAP-Hand 1-4, 1=no disability)
 - ≥20% improvement + absolute change of ≥1 points in disease activity (NRS 0-10, 0=no disease activity)

5.1.3 Secondary Outcomes Definitions

Secondary outcomes are listed in Table 1.

For assessment of cost-effectiveness, we will use healthcare costs (as listed under Costs in Table 1) and scores from EQ-5D-5L calculated into a utility index.

5.1.4 Overview of Outcomes

Table 1 Primary and secondary outcomes

	Data collection instrument and scale	Timepoints
Primary outcome		
Probability of OMERACT- OARSI response	The responder classification is a composite index reported as a single variable (yes/no)	t0, mo, t3, t6
·		
Secondary outcomes		
Hand pain at rest	Pain left/right hand last week, NRS 0-10, 0= no pain	t0, ex, mo, t3, t6
Pain in activity	Pain left/right hand last week, NRS 0-10, 0= no pain	t0, ex, mo, t3, t6
Stiffness	Stiffness left/right hand last week, NRS 0-10, 0= no stiffness	t0, ex, mo, t3, t6
Grip strength	Maximum grip strength, mean of two measures left/right hand, in kg using the JAMAR dynamometer	t0, t3
Activity performance of the hands (hand function)	Measured by the Measure of Activity Performance of the Hand (MAP-Hand); mean of 18 standardized activities, rating scale 1 ("no difficulty") to 4 ("cannot perform")	t0, mo, t3, t6
Health-related quality of life	Measured by EuroQoI EQ-5D-5L, five items (mobility, self-care, usual activities, pain/discomfort, anxiety/depression) scored at five level scare ("no problems" to "unable to do"), calculated as an utility index 0-1, 1= best health-related quality of life. Visual analogue scale (EQ VAS), 0-100, 100= perfect health	t0, t3, t6 a
Global assessment of disease activity	Disease activity last week, NRS 0-10, 0=no disease activity	t0, mo, t3, t6
Global assessment of change	5-point Likert scale from "Much better" to "Much worse"	t3, t6
Quality of care	Modified version of the OsteoArthritis Quality Indicator questionnaire, 15 questions rated as yes/no/unsure or not applicable, scored as pass rate 0-100, 100=best quality of care	t0, t3, t6
Motivation for hand exercises	NRS 0-10, 10=highly motivated	t0, t3, t6
	Statistical Analysis Plan	
	Happy Hands Pa Diakonhiemmet Hospital	age 19 of 27

Hand exercises	Approximately number of exercise sessions each week for the last 3 months	t3, t6
Costs		
Healthcare use	Number of consultations with healthcare providers last 3 months	t3, t6
Medication use	Type and dosage last 3 months	t0, t3, t6
Hand surgery	Conducted hand surgery last 3 months (yes/no), if yes, reported sick leave due to hand surgery	t3, t6
Hospitalization	Number of hospital admissions	t3, t6
Medical equipment	Any medical equipment (i.e. hand orthoses, exercise equipment) bought last 3 months (type and cost)	t3, t6
Technical equipment	Any technical equipment (i.e. bread knife, jar key, sissors, electric toothbrush) bought last 3 months (type and cost)	t3, t6
Work status	Reported as yes/no on the following options: working, sick leave, retired, disability pension, work assessment allowance, unemployed, not working, student	t0, t3, t6
Use of the Happy Hands app (inte Usability	ervention group only) Measured by System Usability Scale (SUS), 10 statements scored on a 5-point scale from "strongly disagree" to "strongly agree"	t3, t6
Satisfaction with use of the	NRS 0-10, 10=highly satisfied	t3, t6
Usefulness of the app	NRS 0-10, 10=highly useful	t3, t6
Adherence to hand	Number of exercises conducted	t3, (t6)
exercises Adherence to informational videos	Number of informational videos watched	t3, (t6)
Adherence to quizzes	Number of quizzes answered	t3
Continued use	Plans to continue using the app, measured as yes/no/unsure	t3, t6
Adverse events	Description of any complaints related to hand exercises	t3
Baseline characteristics		
Age	Years	t0
Gender	Female, male, other	t0
Living arrangement	Living alone, living together with someone	t0
Education	Elementary school, high school, university/college <4 years, university/college > 4 years	t0
Smoking	No previously ves	t0
Height	Cm	t0
Weight	Kø	t0
Most troublesome hand	left right hoth	t0
Other painful joints	Hin knee foot/ankle	t0
Previous treatment for HOA	Yes no	t0
Previous hand surgery	Yes no	t0
Comorbidities	,	
	High blood pressure, heart disease, lung disease, allergy, back pain, stroke, cancer, neurological disease, diabetes, metabolic disease, mental disease, kidney disease, liver disease, ulcer, blood disease	tO

Statistical Analysis Plan Happy Hands Diakonhjemmet Hospital

Page 20 of 27

Health Literacy	eHEALS, 5-point scale with a total score ranging from 8 to 40 (higher score representing higher health literacy)	t0
Experience with using technology and digital services	Experience with smartphone, tablets, apps, video consultation, and digital services (Helsenorge.no), measured on a 5-point scale (very poorly to very good) with an additional alternative of 'never tried'	t0
Motivation for digital treatment/follow-up	NRS 0-10, 10=to a large degree	t0

t0=baseline; t3=3 months; t6=6 months; ex=after each exercise session (in the app/intervention group only); mo=monthly (in the app/intervention group only); NRS=numeric rating scale; MAP-Hand=Measure of Activity Performance of the Hand; HOA=hand osteoarthritis

5.2 Analysis Methods

5.2.1 Primary Outcome

5.2.1.1 Primary Analysis

For analysis of the primary outcome a logistic regression with group as independent variable and OMERACT/OARSI response (yes/no) at 3 months as dependent variable will be conducted. The analysis will adjust for study center, the stratification factor used in the randomization. Probability of being a responder as well as risk difference will be calculated using the adjusted risk and risk difference estimators [25].

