2.3 Sample size

The sample size is calculated based on the primary outcome (proportion of OMERACT-OARSI responders) measured at 3 months. An OMERACT-OARSI responder rate between 26-46% is previously shown in hand exercise groups compared to 6-24% in usual care groups [13,14]. The between-group difference in primary outcome is estimated to 20% [15]. To account for multiple testing (primary and key secondary hypotheses), we will use a significance level of 1%, and 90% power. With a between-group difference of 20% and a usual care responder rate of 20%, we need to include 150 patients in each group. To account for a possible drop-out rate of 25% due to the digital nature of the study, a total of 376 patients are needed.

More detailed information is available in the study protocol [12].

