2.4.4 Decision Rule

For the primary outcome, superiority of probability of OMERACT/OARSI response is claimed if the null hypothesis is rejected at the significance level (alpha) of 0.01 (Bonferroni corrected due to multiple testing of one primary and four key secondary hypotheses; 0.05/5= 0.01. The result is deemed clinically relevant if the lower limit of the 95% confidence interval is more than 20% (see figure 2).

A significance level of <0.01 will also be used for the four key secondary hypotheses due to multiple testing.

For the additional secondary outcomes, multiple testing adjustment will not be carried out. The listed hypotheses will be assessed by their (unadjusted) p-values though no formal acceptance/rejection of these hypotheses will be done.

The intervention will be considered cost-effective if the incremental cost effectiveness ratio is below the threshold for cost-effectiveness, recommended in Norway. In the health economic evaluation, we will not consider p-values or confidence intervals for the ICER but instead plot bootstrapped ICERs on the cost-effectiveness plane and calculate a cost-effectiveness acceptability curve [16].

Statistical Analysis Plan Happy Hands Diakonhjemmet Hospital

Page 11 of 27

Figure 2: Visualization of superiority and clinically relevant difference.

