5.2.1.5 Missing Data

We are expecting the amount of missing data to increase with time, but we cannot retrace the individual reasons for missingness. The primary analysis will utilize multiple imputation, including variables such as gender, age, pain, function and disease activity at baseline and 3 months.

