5.2.1.6 Sensitivity Analyses

Statistical Analysis Plan Happy Hands Diakonhjemmet Hospital

Page 21 of 27

Kommentert [[name]]: Skal center justeres for? Vanlig å justere for stratifiseringsvariabler brukt i randomiseringen.

For the primary endpoint, a sensitivity analysis will be carried out adjusting for recruitment site (, baseline pain, disease activity and function (which are the measures included in the OMERACT/OARSI responder criteria). Additional sensitivity analyses may be conducted, adjusting for variety in usual care (participating in osteoarthritis courses).

If deemed necessary, sensitivity analyses will also be conducted to address missing data and subgroup data.

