5.2.2 Secondary Outcomes

5.2.2.1 Secondary Analyses

a) OMERACT/OARSI responders at 6 months
For the secondary outcome of probability of OMERACT/OARSI response in the two groups at 6 months, we will conduct the same analysis as for the primary outcome.

Secondary continuous outcomes will be analysed using linear regression. The analyses will, in addition to randomization group, adjust for baseline level of the outcome and study center. Missing values will be handled using multiple imputation.

b) Health economic evaluation

Aim: To assess whether the Happy Hands app in combination with usual care is a cost-effective treatment strategy for patients with hand OA compared to usual care alone.

Statistical software: Mainly STATA. Excel for bootstrap, plotting results on the cost-effectiveness plane and for construction the cost-effectiveness acceptability curve.

Perspective on costs: health care perspective as primary analysis, inclusion of production loss in explorative analysis.

Cost of the intervention: The Happy Hands app is not yet commercially available, hence has no official list price or yearly fee. Based on the cost of development and maintenance and the size of the eligible patient population, we assume that the app will be offered at an annual subscription fee of NOK 150 (EUR 13).

Identification of resources: patient self-reported in questionnaire, asked about resource use items as displayed in Table 1.

Measurement of resource use: patient self-reported in questionnaire. May add information from clinical expertise if needed, e.g. patient reports a rehabilitation stay, but not duration.

Statistical Analysis Plan Happy Hands Diakonhjemmet Hospital

Page 22 of 27

Valuation of resource use data: As far as possible, we will use unit prices reported in the Directorate of Medical Products database for use in health technology assessments (https://view.officeapps.live.com/op/view.aspx?src=https%3A%2F%2Fwww.dmp.no%2Fglobalassets %2Fdocuments%2Foffentlig-finansiering-og-pris%2Fdokumentasjon-tilmetodevurdering%2Fenhetskostnader-v1.5.xlsx&wdOrigin=BROWSELINK), this includes the price per in-patient day at hospital.

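### The primary responder model adjusts for centre only; adding the three baseline scores would be a small, essentially free gain (about 0 to 3 points of power), not the correction of an error

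*SAP*

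**What the plan says.** SAP 5.2.1.1 specifies a logistic regression of 3-month response on group. On covariates it says: "The analysis will adjust for study center, the stratification factor used in the randomization". On the effect measure it says: "Probability of being a responder as well as risk difference will be calculated using the adjusted risk and risk difference estimators".

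The baseline scores appear in three other places:

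- **Sensitivity analysis (5.2.1.6):** "For the primary endpoint, a sensitivity analysis will be carried out adjusting for recruitment site (, baseline pain, disease activity and function". The SAP gives its reason, that these are the components of the responder rule.
- **Missing data (5.2.1.5):** "The primary analysis will utilize multiple imputation, including variables such as gender, age, pain, function and disease activity at baseline and 3 months".
- **Continuous secondary outcomes (5.2.2.1):** "The analyses will, in addition to randomization group, adjust for baseline level of the outcome and study center".

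The claim of superiority follows the primary analysis. Under 2.4.4, "superiority of probability of OMERACT/OARSI response is claimed if the null hypothesis is rejected at the significance level (alpha) of 0.01". Randomisation is stratified by site only (2.2), and 4.3 says that important baseline imbalance will be noted; it does not say that it will be adjusted for.

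**The concern.** The responder rule (5.1.2) requires both a percentage and an absolute change on bounded scales, so the starting value can put some criteria out of reach:

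- If percentage change is taken on the raw 1-to-4 MAP-Hand score, a patient starting below 2.0 cannot improve by 50%, because half of the baseline lies below the scale minimum of 1.
- A patient starting below 1.3 cannot improve by 0.3 points.
- A baseline pain below 2 rules out the high-improvement pain criterion.

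Some dependence of response on baseline is therefore plausible, though its strength is unknown. If it exists, the centre-only test is slightly less precise than the data allow, and a chance difference between arms in these scores passes into the responder difference. If the centre-only and baseline-adjusted results fell on opposite sides of 0.01, the decision rule would follow the model with less information. Preferring the other one at that stage would not be credible.

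**Working it through.** **Inputs from the SAP.** Response 20% vs 40%, alpha 0.01, power 90%, 150 per group, 25% drop-out, total 376 (2.3); 1:1 allocation and 20 sites (2.2). Sidedness is not stated. Two-sided is assumed because it comes close to the stated size; one-sided gives 135 per group.

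**Step 1. Reproduce the plan's figure.** With z = 2.576 and 1.282:

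- Unpooled: n = (2.576 + 1.282)² × (0.2×0.8 + 0.4×0.6) / 0.20² = 148.8, so 149 per group.
- Pooled: n = [2.576×√(2×0.3×0.7) + 1.282×√0.40]² / 0.20² = 153.7, so 154 per group.

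The stated 150 lies between them. It comes from a plain two-proportion comparison and relies on no gain from covariates.

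**Step 2. How strongly might the baselines predict response?** The SAP gives no figure, so this is an assumption. The 5.1.2 rule was applied to simulated scores: pain and disease activity mean 5, SD 2; MAP-Hand mean 1.9, SD 0.45; correlations between scores 0.5 to 0.6. The share of within-arm responder variance explained by the three baselines (R²) was:

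| Baseline-to-follow-up correlation | R² at 20% response | R² at 40% response |
|---|---|---|
| 0.4 | 0.064 | 0.082 |
| 0.5 | 0.042 | 0.056 |
| 0.6 | 0.023 | 0.033 |
| 0.7 | 0.007 | 0.013 |
| 0.8 | 0.000 | 0.001 |

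Moving the pain and disease-activity means to 4 or 6 at a correlation of 0.6 gave 0.025 to 0.050. The working range is about 0 to 0.08.

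**Step 3. Convert R² to power.** Effective n = n/(1 − R²), and power = Φ{[0.20×√n_eff − 2.576×√0.42] / √0.40} (pooled variance). At 150 per group:

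| R² | Effective n per group | Power |
|---|---|---|
| 0 | 150 | 89.1% |
| 0.02 | 153 | 89.8% |
| 0.05 | 158 | 90.9% |
| 0.08 | 150/0.92 = 163 | 91.9% |

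The gain is 0 to 2.8 points. If only 376 × 0.75 = 282 patients (141 per group) were evaluable, power would go from 86.8% to 89.9% over the same range (pooled), or from 88.1% to 91.0% (unpooled).

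**Step 4. Check by simulating the planned analysis.** Logistic regression with standardised risk difference, 300 patients, 20 sites:

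| R² | Centre only | Centre + three baselines |
|---|---|---|
| 0 | 89.7% | 89.7% |
| 0.05 | 89.5% | 91.4% |
| 0.11 (beyond the Step 2 range) | 88.7% | 92.1% |

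Under the null, the test of the group coefficient rejected in 1.0 to 1.1% of runs and the risk-difference test in 1.2 to 1.4%, for both models. With 3,000 runs the Monte Carlo standard error is √(0.01×0.99/3000) = 0.18 points, so no cost of adjustment is visible, even at R² = 0.

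**Step 5. Size of a chance imbalance.** The standard error of the risk difference at 150 per group is √(0.40/150) = 0.0516. A one-SD chance imbalance in the prognostic part of the baselines shifts the risk difference by √R² × 0.0516. This is 0.7 percentage points at R² = 0.02, 1.5 points at R² = 0.08, and nothing at R² = 0, against a planned difference of 20 points.

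**The case against.** The case for leaving the plan alone is substantial:

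- **The analysis is sound.** It adjusts for the stratification factor, holds its error rate and has about the planned power at 150 per group. Randomisation and the 1% test already allow for chance imbalance, and Step 5 shows that its likely effect is small. All of this stands.
- **The gain may be nil.** The assumed range for R² includes zero. This also stands.
- **The secondary outcomes are a different case.** There, a continuous score is adjusted for its own baseline, where correlation is direct. A dichotomised composite of changes need not be handled the same way. A reader might infer that the plan contradicts itself here; it does not.
- **The adjusted model is already prespecified.** True, so a material baseline effect would be seen and reported. But the decision rule in 2.4.4 reads the primary analysis, so the sensitivity analysis makes the information visible without using it in the confirmatory test.
- **Baseline pain is not one variable.** Pain is recorded for each hand, at rest and in activity (5.1.1.15, Table 1), so the covariate has to be named before it can be used. This is correct and is part of the fix. The existing sensitivity analysis needs the same choice.

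A reader might also infer that the confirmatory test is materially underpowered or biased for want of these covariates. The SAP does not support that. It gives no prognostic strength, and its sample size never counted on covariate gain. A power such as 91.7% at 141 per arm (unpooled) needs R² = 0.10, which is outside the simulated range.

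**Conclusion.** This is an optional improvement of low to moderate weight. The centre-only primary analysis is not an error. That the baselines are left out of the confirmatory model, and that including them does no harm, is well supported. The size of the benefit is not: about 0 to 3 points of power, with R² of about 0 to 8%, rests wholly on assumed means, SDs and correlations.

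The argument for change is that the downside is negligible: three degrees of freedom and no measurable loss of power or error control, even when the scores predict nothing. The target is unchanged as long as it remains the standardised risk difference. An odds ratio from the enlarged model would be conditional on more covariates and so not directly comparable with the centre-only one.

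**What to change.** Before outcome data are analysed by arm, amend SAP 5.2.1.1 and 5.2.1.6 as follows:

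1. Primary model: logistic regression of response on group, centre, baseline pain, baseline MAP-Hand and baseline disease activity.
2. Name the pain score (hand or hands, at rest or in activity) and use the same one in the responder rule and as the covariate.
3. Keep the adjusted risks and standardised risk difference as the reported effect.
4. Apply the same model to response at 6 months, which 5.2.2.1 already ties to the primary analysis.
5. Report the centre-only model as the sensitivity analysis.

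The cost is a few sentences of SAP wording and one definitional choice about pain. No new data are needed, and the imputation model already lists these baseline scores. The sample size does not change.
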